### **3. Abstract**

Color vision deficiency is common among males and can impact medical care in a number of ways, including limiting a provider's ability to note certain physical signs, interpret stool guaiac or urine dipstick tests, and to identify colors under a microscope. While this deficiency does not preclude a career in medicine, many such providers will develop "work-arounds" such as involving colleagues with normal color vision to care for their patients. This study seeks to understand whether products made by EnChroma to improve color vision will have a positive impact on patient care. Color vision deficient (CVD) providers in the emergency department will be identified using a screening test and then formal vision testing. These CVD providers will receive EnChroma products to utilize during patient care and will be surveyed on their experience.

### **4. Introduction and Background**

Color discrimination is important in many careers but is particularly important in medical fields where decisions may be based on the ability to rapidly detect deviations in blood color, pallor or other important clinical signs. Color vision deficiency is the inability to distinguish certain shades of color and can range in severity from mild to severe. The most common form is red-green (representing both deutan and protan defects) which has an X-linked recessive inheritance pattern, thus affecting mostly males. Red-green color vision deficiency affects approximately 1 in 12 men and 1 in 200 women in the world. There are other more rare and more severe forms such as blue-yellow defects (also called tritan defects) and blue cone monochromacy which results in poor visual acuity and extremely reduced color vision. As red-green CVD is by far the most common form, research has primarily focused on subjects with this form.

Prior work has demonstrated that medical students and physicians are affected by CVD. This has a number of effects on the practice of medicine by CVD individuals, including: impaired ability to recognize abnormalities in stool guaiac tests, blood tests, urine tests, histologic stains, and ophthalmoscope exams, as well as impaired ability to detect skin color changes due to cyanosis, jaundice or erythema, and rashes. There have also been case reports of providers with CVD failing to identify rectal bleeding resulting in a delay in treatment. However, anecdotal reports demonstrate multiple "work-arounds" that CVD providers employ to minimize direct effects on patient care. The vast majority of "work-arounds" reported involve peer corroboration in areas where color differentiation is important. There is a lack of evidence regarding the effect of provider CVD on patient outcomes.

In addition to impacting patient care, CVD can also impact medical students' education by increasing difficulty with pathology and slide identification as well as anatomy as it impairs one's ability to distinguish certain tissues during dissections. Prior studies have also demonstrated that CVD impairs medical students' ability to detect color differences in the fundus during retinal exams. Standardized exams during medical school also include color identification on histological stains on pathology slides. These difficulties as well as others have led some students to avoid certain medical specialties. In

addition to improving patient care, it may also be possible to reduce disparities in medical school performance and choice of specialty caused by CVD.

EnChroma (Berkeley, CA) has developed multiple products which improve brightness and color purity of primary colors for CVD people. While the manufacturer has reported the effectiveness of these products in aiding color vision, they have not yet been shown to cure color vision deficiency, and there is individual variation in the response to the glasses given varying degrees of severity and type of CVD. However, they have not been evaluated yet in a clinical setting to assess their impact on patient care by CVD healthcare providers. Even an incremental increase in a physician's ability to detect a subtle difference may improve that provider's ability to identify a critical examination finding. Thus, the long term goal of the present study is to improve patient care by mitigating the deleterious effects of CVD in a clinical setting.

## **5. Study Aims and Outcomes:**

**Aim:** Evaluate the feasibility of using EnChroma glasses in a patient care environment, as well as subjective reflections on the effects of the product on patient care. CVD providers will wear the glasses for 2 weeks. Providers and patients will be surveyed on the comfort of the product, any subjective influence on color vision overall, specific examples of improvements or hindrances to patient care, and overall impression providing evidence for safety and effectiveness of the product in the patient care setting.

**Hypothesis:** CVD providers will consider EnChroma products to be unobstructive to their daily work and without adverse effect on patient care.

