#### **METHODS**

Each participant with CVD (other than medical students) will be provided EnChroma products to use indoors over the course of two weeks in the emergency department, educational settings, and in their personal life. They will be encouraged to wear the glasses for at least 10 hours over 1-2 weeks prior to wearing them in a clinical setting to adjust to their use, and for 10 minutes before beginning patient care as per manufacturer instructions. They will be encouraged to take specific note of clinical scenarios that require the use of color vision (e.g., - rashes, tympanic membrane erythema, stool guaiac

testing, etc.). Placebo glasses will not be provided given that subjects will not be able to be blinded to the difference, and subjects are unlikely to tolerate red tinted glasses which do not provide benefit. The participant will then complete a survey regarding their baseline experience of having CVD, and the participant's reflections on how CVD has affected his/her clinical practice and education in the past, including any "work-arounds" they have employed previously. The survey will also ask them to reflect on the impact of the glasses on patient care as well as a 100mm scale in addition to open ended questions.

Data will be analyzed both quantitatively (improvement on 100mm visual analog scale and any change in patient survey responses) as well as qualitatively, using thematic analysis of open ended survey data within the grounded theory paradigm.

In the event of substantial missing data, data will be imputed using a multiple imputation procedure. The type of procedure and the number of imputed data sets will be determined by the amount of missing data and the pattern of missingness. However, we do not expect significant missing data in this study. No data will be sent to the FDA.

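### The aim says survey impressions will provide evidence of safety and effectiveness in patient care, but the planned care data can show only perceived effect

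*Combined protocol and SAP*

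**What the plan says.** The aim in section 5 (Study Aims and Outcomes) opens with feasibility and subjective reflections. It names the informants: "Providers and patients will be surveyed on the comfort of the product, any subjective influence on color vision overall". It goes on to specific examples of help or hindrance to care, and closes with an "overall impression providing evidence for safety and effectiveness of the product in the patient care setting". The hypothesis that follows is about opinion: "CVD providers will consider EnChroma products to be unobstructive to their daily work and without adverse effect on patient care".

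The METHODS part of section 6 gives the quantitative analysis as "improvement on 100mm visual analog scale and any change in patient survey responses", with thematic analysis of the open-ended answers. On clinical use it says of participants: "They will be encouraged to take specific note of clinical scenarios that require the use of color vision". It also explains the lack of a control lens: "Placebo glasses will not be provided given that subjects will not be able to be blinded to the difference".

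Section 4 (Introduction and Background) lists among the effects of the deficiency "impaired ability to recognize abnormalities in stool guaiac tests, blood tests, urine tests", and adds: "There have also been case reports of providers with CVD failing to identify rectal bleeding resulting in a delay in treatment".

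**The concern.** The closing phrase of the aim claims more than its opening. Feasibility, comfort and reflections are matters of experience. Safety and effectiveness in patient care depend partly on whether color-dependent findings are read correctly, and the protocol's own background gives missed findings as the reason the deficiency matters.

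The people asked whether care suffered are those whom the protocol describes as less able to see the signs in question, together with patients who will often have no way to judge. A favorable survey could therefore sit alongside misread signs that nobody reported. The wearers also know they are wearing the product, so a favorable rating cannot be separated from expectation.

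What is at stake is the conclusion. Section 4 says the products have not yet been evaluated in a clinical setting, so a report that repeats the aim's wording would claim something the data do not establish.

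**Working it through.** The point depends on no stated figure, so the check sets the claim against each planned source of data.

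1. **The claim.** Section 5: survey impressions are to give evidence of safety and effectiveness in the care setting.

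2. **Self-rated 100mm scale and open-ended answers (METHODS).** These record the wearer's view of the glasses' impact on care. They are unblinded, and no placebo lens is used. They measure perceived effect.

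3. **Patient surveys (section 5, METHODS).** These record the patient's view. Neither section links them to a reference reading of any finding. They also measure perception.

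4. **Notes on color-dependent scenarios (METHODS).** Participants are encouraged to notice such scenarios. The text does not ask whether the reading was right, does not name a comparator and does not include the notes in the quantitative analysis.

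5. **D15 and HRR, with and without glasses (section 6, Study Population).** These are objective, and they compare the two conditions within each person. They are confirmatory color vision tests at entry. They can show a change in color discrimination but not whether findings in care were read correctly.

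6. **Removal of the glasses (section 6, Study Participant Risk).** Participants are encouraged to take the glasses off if they feel care is hindered. This depends on the same perception as the survey and is not described as an outcome.

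7. **Peer corroboration (section 4).** The background says most reported work-arounds involve colleagues. This could bring some misreadings to light, but it is described as past practice and not as a study procedure or data source.

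8. **Power (section 7).** The stated 80% power with 50 participants for a standardized difference of 0.44 concerns the glasses-on versus glasses-off contrast, on an endpoint that the sentence does not name. It gives no assurance about unnoticed errors.

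Items 2 to 4 are the only information on care, and none of them contains an accuracy or error outcome. Item 5 is objective but is not about care. Items 6 and 7 are not data. Nothing planned therefore connects the surveys to the claim in item 1.

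**The case against.** The strongest reply is that this is a feasibility study. The aim says so, the hypothesis asks what providers will consider, and the risk section names comfort and the ability to give care with the glasses on as a key question. A survey measures all of that. This stands: a reader might infer that the design cannot test its own hypothesis, and the documents do not support that. The overreach is confined to the closing phrase of the aim.

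A second reply is that wearers and patients are not blind to every error. Colleagues, later results or the patient may reveal a misreading, and the survey invites examples of hindrance to care. The survey itself is not in the documents, so what it asks about correctness is unknown. This also stands in part. It would be too strong to say that providers and patients cannot tell; they may often not notice. None of the routes by which an error might surface is a planned data source.

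Third, the study is not wholly subjective, since D15 and HRR are done in both conditions. That is true of color discrimination and does not extend to care.

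Fourth, the protocol gives a reason for having no placebo lens, the glasses are described as non-significant risk and are already on sale, and no data go to the FDA. These facts support running the study as designed. They do not turn impressions into evidence of safety.

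**Conclusion.** The point holds for one phrase. The aim in section 5 gives the surveys a property that the design does not have. The feasibility aim, the comfort questions and the hypothesis about providers' opinions are unaffected.

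No numerical size is given. A reader might want an upper bound on misread signs after zero reports, but the documents give neither the number of color-dependent findings per provider nor the share of misreadings that wearers recognize. Findings would also cluster within providers. Any such bound would cover all misreadings and not only those due to the glasses, because section 4 says that these providers already have difficulty with colored signs. Nor do the documents show that the glasses cause harm; the point is that the planned data could not settle the question either way.

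The conclusion rests on two things: the survey content being as summarized in section 5 and METHODS, and section 4 being right that recognition of colored signs is impaired in this population. If the survey instrument does collect verified errors, the protocol should say so, and the point would weaken. This does not prevent the study from running, but the phrase should be changed because it governs what may be concluded.

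**What to change.** In section 5, keep the overall impression as an item, but replace the claim attached to it in "overall impression providing evidence for safety and effectiveness of the product in the patient care setting" with wording such as: *describing the effect of the product on patient care as perceived by providers and patients*. Add a sentence saying that any result of no adverse effect will be reported as perceived only. Where D15 and HRR results are reported, describe them as evidence on color discrimination.

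If the notes on color-dependent scenarios are collected in structured form, use them descriptively. An agreement analysis by glasses on or off is not recommended. Wearing is at the participant's discretion and may stop when care seems hindered, so the comparison would be confounded. It would also cover only the selected findings that someone else happened to check.

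The cost is a short edit and a weaker stated conclusion. No procedure, sample size or analysis changes.

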#### *Study Participant Risk*

The devices proposed for testing from EnChroma meet the FDA criteria for non-significant risk devices. The glasses pose no serious risk to the health, safety, or welfare of a subject, and they are not of substantial importance in diagnosing or treating disease. Healthcare providers are free to remove or discontinue use of these devices while performing patient care if they are hindering patient care in any way, reverting to their usual care. Furthermore, the glasses are currently available to the public without prescription and providers are able to purchase and wear them during patient care without approval. As such, we do not anticipate any substantive risk to patients while these are worn during patient care. We will encourage participants to remove the glasses if they feel their medical care is being hindered in any way. Of note, the indoor Enchroma glasses do diminish total light transmission somewhat (50% visible light transmission) and a key question in this study is whether that has a significant effect on providers' comfort and ability to deliver care without removing the glasses.

There is a risk of breach of confidentiality, albeit low. No personal identifying information will be collected about the patients examined as part of this study. Data will be aggregated before analysis.

Records of any ophthalmologic examinations performed on entry into the study will be maintained by study staff and destroyed at the end of data analysis. Any new pathologic conditions discovered during that examination will be reported to the subjects so that they may seek medical care as needed.

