## 7. Participant Selection

- **Sample Size Calculation.** Given the number of male providers in Emory's department of Emergency Medicine, and the prevalence of CVD in the general populations, the maximum achievable sample size is expected to be approximately 50 participants. A sample size of 50 will provide sufficient power (80%) to detect a within-group standardized difference (Cohen's  $d$ ) of 0.44 between the glasses-on and glasses-off conditions.
- Inclusion/Exclusion Criteria

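### The only hypothesis is that providers find the glasses unobstructive and harmless to care, but no planned quantitative result says how many did, or how many stopped wearing them

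*Combined protocol and SAP*

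**What the plan says.** Section 5 (Study Aims and Outcomes) gives a feasibility aim and a single hypothesis: "CVD providers will consider EnChroma products to be unobstructive to their daily work and without adverse effect on patient care". Providers and patients are to be surveyed on comfort, perceived influence on color vision, examples of help or hindrance, and overall impression.

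Section 6, METHODS, describes a provider survey completed after the wearing period. It asks about the impact of the glasses on care, "as well as a 100mm scale in addition to open ended questions". The quantitative analysis is "improvement on 100mm visual analog scale and any change in patient survey responses"; the open answers are analyzed by theme. For missing data: "In the event of substantial missing data, data will be imputed using a multiple imputation procedure". On who gets the glasses: "Each participant with CVD (other than medical students) will be provided EnChroma products to use indoors".

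Section 6, Study Participant Risk, says "We will encourage participants to remove the glasses if they feel their medical care is being hindered in any way". It describes as a key question whether reduced light transmission affects providers' "comfort and ability to deliver care without removing the glasses".

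Section 7, Sample Size Calculation: "A sample size of 50 will provide sufficient power (80%) to detect a within-group standardized difference" (Cohen's d of 0.44, glasses on versus off). It does not name the measure, the test, or the significance level. Fifty is described as about the most that can be recruited.

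**The concern.** The hypothesis is about acceptability and absence of harm. The planned quantitative result and the power statement are about a difference. A mean change on a visual analog scale does not answer how many providers found the glasses unobstructive, and it can hide a minority whose work was hindered. Taking the glasses off for good because they got in the way is the most direct sign that the hypothesis fails for a provider. The risk section ties removal to a key question, yet METHODS lists no removal or stopping result. The general imputation rule does not say how someone who stopped is treated, so that person could be given an imputed score rather than counted as a failure.

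At stake is the main claim of the study. It could report a mean change and a set of themes and still have no figure, with its uncertainty, for the statement it set out to examine.

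**Working it through.** **1. Hypothesis against planned results**

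| Part of the question | Planned quantitative result | What it can show |
|---|---|---|
| Unobstructive to work | None named | Themes and comfort topics describe it; nothing counts it |
| No adverse effect on care | Mean scale change, if the scale rates impact on care (the wording is loose) | Average direction; not how many were hindered |
| Care delivered without removing the glasses | None named | Comfort is surveyed; removal and stopping are not named |
| Patient responses | Any change | The patients' view, whereas the hypothesis is about what providers consider |

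**2. The plan's own figure**

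Inputs from section 7: n = 50, d = 0.44, power 80%. Assumed, because not stated: paired t-test, two-sided 5%.

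- Noncentrality = d × √n = 0.44 × √50 = 3.11, with 49 degrees of freedom and critical value 2.01.
- Power = 86.2%, not 80%. The difference detectable with 80% power is d = 0.404.
- Unstated choices come close to 80%: two-sided alpha of 0.025 (78.5% by t, 80.8% by normal approximation), or about 15% dropout leaving 42 completers (79.5%).

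The figure is therefore under-specified rather than shown to be wrong. Under every variant it is power to detect a difference; it gives no precision for a proportion.

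**3. What a null difference would be worth**

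This uses the same assumed test and treats the unnamed measure as one on which harm would show.

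- Half-width of the 95% interval for a mean difference = 2.01 / √50 = 0.28 SD.
- True worsening of 0.2 SD: non-significant 71.6% of the time. True worsening of 0.3 SD: 45.2%.
- True worsening of 0.44 SD: detected 86.2% of the time, so a clear average harm could be seen.
- At an assumed n = 30, since 50 is the ceiling: non-significant 81.5% (0.2 SD) and 64.5% (0.3 SD).

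**4. What the matching analysis would give**

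Exact (Clopper-Pearson) 95% limits for x successes in n: lower = Beta quantile 0.025 with parameters (x, n − x + 1); upper = Beta quantile 0.975 with parameters (x + 1, n − x). The counts are illustrations; the documents give no acceptability rate.

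| Successes / n | Proportion | 95% CI |
|---|---|---|
| 45/50 | 90% | 78% to 97% |
| 40/50 | 80% | 66% to 90% |
| 27/30 | 90% | 73% to 98% |

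**5. Why the denominator must be fixed**

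Suppose 50 are issued glasses, 45 have a known outcome and 42 of these are successes.

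- Known outcomes only: 42/45 = 93% (82% to 99%).
- All issued, with the 5 unknown counted as not successful: 42/50 = 84% (71% to 93%).

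The lower limit moves by 11 percentage points (82 − 71) on a choice the plan leaves open.

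**The case against.** The strongest reply is that this is a feasibility study of perceptions. A thematic analysis of providers' own accounts is a fair match to a hypothesis about what they consider, and descriptive reporting is enough. That stands in part: no formal test or success threshold is required. But a proportion with its interval is itself descriptive, and themes cannot say how common a problem was.

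Second, the plan is not silent on harm. Comfort, hindrances and overall impression are surveyed, and a clearly positive rating of impact on care would argue against average harm. That also stands. The gap is firm for obstruction, for how many individuals were hindered, and for stopping. It is weaker for the average effect on care. The survey form is not in the documents, so suitable closed items may already exist; even so, METHODS names no acceptability or stopping result drawn from them.

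Third, the power figures in step 3 rest on an assumed test of an unnamed measure. The only with-and-without measurements described are the two color vision tests at entry, which do not measure harm. The figures are therefore a caution, not a measure of the defect.

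A reader might infer that the investigators mean to take a non-significant difference as proof of no adverse effect, or that the study cannot speak to harm at all. The documents support neither. They never propose that reading of a null result, and both a clear worsening and the qualitative material could contradict the hypothesis.

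**Conclusion.** The concern holds in a limited form and should be fixed. As written, the plan's quantitative results address change, while its one hypothesis addresses acceptability and absence of harm. No planned figure gives the number of providers who found the glasses unobstructive, were hindered, or stopped because of them. The study remains useful as qualitative and feasibility work.

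The size of the gap cannot be put as a single number, because the plan attaches no rate or margin to its hypothesis. Two figures frame it. At 50 participants the missing proportion would have been estimated usefully (78% to 97% around 90%), so sample size is no reason to leave it out. And an unspecified treatment of 5 non-responders could move the lower limit from 82% to 71%. Both rest on illustrative counts. METHODS expects little missing data, in which case the second effect would be smaller.

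**What to change.** In METHODS:

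- Make the main quantitative result the number and proportion, with an exact 95% confidence interval, of all participants issued glasses for clinical use who meet both conditions: they rate the glasses unobstructive and without adverse effect on care on closed items, and they did not stop clinical use because of the glasses.
- Count those who stopped because of the glasses as not successful; do not impute them.
- Use one primary denominator: everyone issued glasses for clinical use, with non-responders counted as not successful. Give the proportion among those with a known outcome as a sensitivity analysis, and report the number of non-responders.
- Report the visual analog scale and the patient responses as secondary, and state that a null change on the scale will not be read as no adverse effect.

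In section 7, name the measure, test and significance level behind the power statement.

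An acceptable proportion fixed in advance by the investigators is optional for a feasibility study. If one is wanted at n = 50, a lower limit above 70% needs 42 successes (94% chance if the true rate is 90%). One above 80% needs 46 (43% chance at a true 90%, 90% at a true 95%).

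The cost is a few closed survey items, if the form lacks them, some protocol wording and a more modest claim. No extra participants are needed, though the interval widens if fewer than 50 are issued glasses. The change defines an outcome only; it leaves untouched when providers may remove the glasses.
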